### 3-week Post-Procedure Visit:

#### All patients at 3-week post-procedure visit will receive:

- a. AUA-SI, PPBC, OABq-SF, PPBC (per standard clinical practice)
- b. PVR (per standard clinical practice)
- c. UA (per standard clinical practice)
- d. Urine culture if determined necessary by physician (per standard clinical practice)

e. Post-Botox 3-Week Post Procedure Survey

**Symptoms Assessment:** Participants will complete standardized, validated questionnaires documenting urinary symptoms and quality of life for comparison. Instruments will include the American Urologic Association Symptom Index (AUA-SI), Overactive Bladder Questionnaire short-form (OABq-SF), Patient Perception of Bladder Control questionnaire (PPBC) and the Patient's Global Impression of Improvement (PGII).

**Urinary tract infection:** Patients will be assessed at a 3-week follow up visit with urinalysis. If a patient reports symptoms concerning for UTI, urine culture and antibiotic treatment will be ordered at the discretion of the clinician. All patients will be provided with instructions for reporting adverse events including clinic nurse contact information should symptoms of UTI develop. Given that our institution is a tertiary referral center and patients may report to local providers, a system will be in place to obtain all outside urine culture and antibiotic records for analysis.

**Note:** For the purposes of this study, UTI will be defined as  $\geq 10^5$  bacterial colonies in the presence of symptoms.

**Treatment success:** Patients will be assessed at post-procedure appointments at 3 weeks and a phone call at 3 months. Follow up visit will consist of urinalysis, ultrasound PVR, patient-reported questionnaires, and recording of adverse events. Efficacy of injection will be assessed via inter-injection times for patients receiving multiple injections and will be followed for the duration of the study period.

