**Urinary tract infection:** At enrollment, patients will complete a medical history questionnaire which will include information related to prior UTIs. Eligible patients will provide urine specimen for analysis along with physician assessment. Diagnosis of symptomatic UTI prior to injection is to be made at the discretion of the clinician with exception of nitrite positive urinalysis. Patients with nitrite positive urine on the day of injection, regardless of symptoms, will be excluded from enrollment. Nitrite positive urinalyses will be sent for urine culture, and patients may be enrolled in the trial at a later date following treatment. On the day of injection a voided urine specimen will be obtained from all patients and sent for urine culture. This allows for assessment of the bladder milieu at the time of injection, however will not be used for treatment purposes unless patient subsequently becomes symptomatic. Post-void residual will be obtained, per standard clinic protocol, for all patients receiving treatment. This will be done with bladder scanner in clinic and with catheterized specimen for patients receiving an injection in the operating room if PVR not previously recorded in the medical record within 8 weeks prior to injection.

**Assessment of overactive bladder:** Participants will complete baseline standardized, validated questionnaires documenting urinary symptoms and quality of life. Instruments will include the American Urologic Association Symptom Index (AUA-SI), Overactive Bladder Questionnaire short-form (OABq-SF), Patient Perception of Bladder Control questionnaire (PPBC) and the Patient's Global Impression of Improvement (PGII).

**Inclusion/exclusion criteria.** Study criteria are listed in the Table. A diagnosis of OAB and the decision to proceed to third line treatment will be determined by clinician according to AUA guidelines.

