#### **Established patients:**

Established patients continuing injection will be screened and consented on the day of presentation for injection. PVR within 8 weeks must be documented in chart. If no PVR documented within 8 weeks, must repeat PVR prior to injection with either a bladder scanner or catheterized value. UA obtained per existing clinic policy. Eligibility determined by provider based on UA and PVR.

Demographic information including comorbidities will be abstracted from patients' electronic medical records, and a focused history and physical will be performed on day of injection.

**Injection protocol:** All patients will undergo injection per a standardized protocol of 1ml injection per site at a concentration of 10 units/ml. For patients undergoing injection in the clinic setting, an intravesical instillation of diluted local anesthetic will be used prior to injection, if no allergy to anesthetic is reported. For those performed in the operating room, anesthesia will be administered per the discretion of anesthesiology team. The number of units injected will be documented and accounted for during analysis by stratifying patients according to the amount of BTX-A injected.

**Antibiotic protocol:** On the day of injection patients will be randomized to either the experimental or control arm according to a computer generated randomization scheme (see explanation of randomization below). Patients randomized to the experimental arm will receive a single dose of trimethoprim/sulfamethoxazole (800/160mg) peri-procedurally. Patients randomized to the control arm will receive one dose of trimethoprim/sulfamethoxazole peri-procedurally and additionally be prescribed trimethoprim/sulfamethoxazole twice daily for three days. Patients who are allergic will receive amoxicillin/clavulanic acid (875/125mg) twice daily for three days. If allergic to both of the above antibiotics, patients will receive 100mg nitrofurantoin BID for three days. Our budget reflects published data regarding our local antibiogram and population estimates for antibiotic allergies.

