### 3-month Post-Procedure Phone Call:

All patients at 3-month post-procedure visit will receive:

- a. AUA-SI, PPBC, OABq-SF, PPBC (per standard clinical practice)
- b. Post-Botox 3-Month Post Procedure Survey

**Symptoms assessment:** Participants will be asked, by phone, standardized, validated questionnaires documenting urinary symptoms and quality of life for comparison. Instruments will include the American Urologic Association Symptom Index (AUA-SI), Overactive Bladder Questionnaire short-form (OABq-SF), Patient Perception of Bladder Control questionnaire (PPBC) and the Patient's Global Impression of Improvement (PGII).

**Urinary tract infection:** Patients will be asked about presence and frequency of UTI including treatment and duration of treatment.

**Treatment success:** Patients will be assessed at post-procedure phone call at 3 months. Efficacy of injection will be assessed via inter-injection times for patients receiving multiple injections and will be followed for the duration of the study period.

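### The primary endpoint needs a culture, but culture after injection is discretionary even in symptomatic patients, and no rule says how an uncultured episode is scored

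*Combined protocol and SAP*

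**What the plan says.** The Statistical analysis plan makes the primary endpoint the presence or absence of UTI 3 weeks after the procedure. The note in the 3-week Post-Procedure Visit section fixes the meaning: "For the purposes of this study, UTI will be defined as" at least 10^5 colonies together with symptoms.

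The same section schedules a urinalysis for every patient at 3 weeks. It does not schedule a culture. Item d of the visit list leaves culture to the physician's judgement, and for symptomatic patients the text reads "If a patient reports symptoms concerning for UTI, urine culture and antibiotic treatment will be ordered at the discretion of the clinician".

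Other information is collected around the endpoint:

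- Initial Visit, Urinary tract infection: "On the day of injection a voided urine specimen will be obtained from all patients and sent for urine culture". The result is kept out of treatment decisions unless symptoms follow.
- 3-week Post-Procedure Visit: "a system will be in place to obtain all outside urine culture and antibiotic records for analysis". Patients also receive instructions for reporting symptoms. Item e is the "Post-Botox 3-Week Post Procedure Survey", whose content is not in the documents.
- 3-month Post-Procedure Phone Call: "Patients will be asked about presence and frequency of UTI including treatment and duration of treatment". No dates are mentioned.

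No section says how a symptomatic episode without a culture enters the yes/no endpoint.

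**The concern.** A 'Yes' requires a colony count, and a colony count requires a culture that the plan does not require after injection. A patient with symptoms who is treated without a culture cannot meet the definition from a post-injection specimen. Such an episode would have to be counted as 'No' or treated as missing, and the plan chooses neither. The definition also gives no time for the specimen, so it is open whether a positive culture from the day of injection, followed by symptoms, would qualify.

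The other sources do not close the gap. Urinalysis gives no colony count. Outside records and the 3-month call can reveal a treated episode, and the 3-week survey may do so, but none can supply a culture that was never taken.

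What is at stake is the comparison with the 10-point margin. If uncultured episodes count as 'No' and the same share is lost under both regimens, both rates shrink in proportion, and so does their difference. A real excess of UTI with PPA is then harder to see.

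**Working it through.** **Inputs from the Statistical analysis plan.** P[infection] 25% with EDA and 35% with PPA; concordance +0.05; type I error 5%; margin 0.10; 68 patients, each receiving both regimens.

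**Assumptions, because the documents give no figure.** Capture c is the share of true UTIs that are cultured. It is equal under both regimens and independent between a patient's two injections. Uncultured episodes count as 'No'. The 25% and 35% are true rates before any loss. The test is a one-sided 5% paired test on 68 pairs; the SAP names no test.

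**Reproducing the plan's variance.** Reading concordance as a 5-point rise in one probability given infection under the other regimen, P(infected under both) = 0.25 × (0.35 + 0.05) = 0.10. Then 0.25 + 0.35 − 2 × 0.10 = 0.40, the SAP's value. Subtracting the squared mean difference gives 0.40 − 0.01 = 0.390, used below. The stated sample size is a separate matter: with variance 0.40 the usual paired formula gives 8.564 × 0.40 / 0.01, or 343 pairs. This point uses 68 only because that is the planned enrolment.

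**PPA tested against EDA.**

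- Observed rates: oE = 0.25c and oP = 0.35c
- Observed difference: D = 0.10c
- Variance: v = oE + oP − 2c² × 0.10 − D²
- False non-inferiority: Φ((0.10 − D)/√(v/68) − 1.645)

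| c | oE | oP | D | v | False non-inferiority |
|---|---|---|---|---|---|
| 1.00 | 0.250 | 0.350 | 0.100 | 0.390 | 5.0% |
| 0.95 | 0.2375 | 0.3325 | 0.095 | 0.380 | 5.7% |
| 0.90 | 0.225 | 0.315 | 0.090 | 0.370 | 6.6% |
| 0.80 | 0.200 | 0.280 | 0.080 | 0.346 | 8.6% |
| 0.70 | 0.175 | 0.245 | 0.070 | 0.317 | 11.4% |

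For c = 0.70: v = 0.175 + 0.245 − 0.098 − 0.0049 = 0.3171, the standard error is 0.0683, and 0.03/0.0683 − 1.645 = −1.206, which gives 11.4%. Across all four scenarios in the SAP's power table the ranges are 6.4–6.6% (c = 0.90), 8.3–8.7% (0.80) and 10.6–11.6% (0.70).

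**EDA tested against PPA, as the SAP words it.** The difference is now −D, and P(declare non-inferiority) = Φ((0.10 + D)/√(v/68) − 1.645). At c = 1 this is Φ(0.20/0.0757 − 1.645) = 84%. At c = 0.70 it is Φ(0.17/0.0683 − 1.645) = 80%.

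**If 25% and 35% are rates as measured,** there is no second loss. A measured 10 points then stands for 10/0.9 = 11.1, 10/0.8 = 12.5 or 10/0.7 = 14.3 points of true UTI.

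**If capture differs by regimen,** the bias has no fixed sign. With 70% capture under PPA and 90% under EDA, a true 10 points appears as 0.245 − 0.225 = 2 points. With the reverse it appears as 0.315 − 0.175 = 14 points.

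**The case against.** The strongest reply is that the loss may be small. Every patient has a urinalysis at 3 weeks, so clinicians decide on culture with that result in hand and may culture most true infections. Patients are told how to report symptoms earlier, and outside cultures are collected. At 95% capture the illustrated rate is 5.7% against 5%. This stands as a reason to treat the larger figures as extreme. It does not remove the gap: episodes before the visit have no scheduled urinalysis, and culture stays optional throughout.

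A second reply is that the inflation depends on the direction of the test. The Antibiotic protocol makes the single dose experimental ("Patients randomized to the experimental arm will receive a single dose of trimethoprim/sulfamethoxazole"), which points to testing PPA against EDA, but the SAP states the reverse. As the SAP is worded, the illustrated cost is only a modest loss of power. This also stands. Which direction is meant is a separate question; the scoring rule is missing under either.

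A reader might infer that the plan scores uncultured episodes as 'No'. It does not say so. Missing is equally open, and the shrinkage figures apply only under 'No'. A reader might also infer that culturing favours one regimen, since no blinding is described. The documents support neither direction.

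**Conclusion.** The gap is real and touches the primary endpoint: a culture-based definition, discretionary culture in the patients who could meet it, and no rule for symptomatic episodes without one. The status of the day-of-injection culture is also unsettled.

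The size is not known. The range of about 5.7% to 11.4% against 5% rests on assumed capture of 95% to 70%, scoring as 'No', equal loss under both regimens, 25%/35% as true rates and PPA tested against EDA. The documents do not support reading 11.4% as the trial's expected error rate; it needs 30% of UTIs to go uncultured. The change is worth making because it improves what the trial measures at small cost. Confidence in the gap is high; confidence in its numerical effect is limited.

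**What to change.** 1. For outcome measurement, obtain a urine culture from every patient who reports UTI symptoms to the study clinic from injection through the 3-week visit. Use the urinalysis sample where there is one. Treatment decisions stay as the protocol has them.
2. State in the SAP that the qualifying culture must be taken after injection, and how a symptomatic episode that still lacks a culture is scored.
3. Pre-specify one sensitivity analysis that counts symptomatic, antibiotic-treated, uncultured episodes within the 3-week window as UTI. It would draw on clinic records, outside records and the 3-month call, with one date question added to the call. It supplements the primary analysis.

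**Cost.** With 68 × 0.25 + 68 × 0.35 = 40.8 true UTIs and 95.2 injections without UTI, extra cultures are (1 − c) × (40.8 + 95.2s), where s is the share of non-UTI patients who report symptoms. Assuming c of 70–90% and s of 20–40%, this is 6.0 (c = 0.9, s = 0.2) to 23.7 (c = 0.7, s = 0.4) over 136 injections. That is an upper range: episodes treated elsewhere would not come to the study clinic for culture. Episodes before the 3-week visit need an off-visit sample. The rest is a few SAP sentences, one question and one analysis.

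**Downside.** Episodes treated elsewhere may still lack a culture, and recall at 3 months may misdate them. The sensitivity analysis will count some episodes that are not UTI. If item 1 is not adopted, and all uncultured symptomatic episodes are treated and found, these are (1 − c) × s = 2% to 12% of non-UTI patients per regimen, and a true 10 points reads as 9.8 to 8.8. Fewer such episodes remain if item 1 is adopted.

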### 2nd Injection:

Patients will have been consented at the beginning of the study to include both 1st and second injections and therefore do not need to be re-consented. The exact protocol is followed as stated above, however, patients will receive the treatment from the arm NOT received after the first injection. For example, patients who received extended 3 day course of antibiotics after the first injection, will receive only peri-procedural antibiotics after the 2nd injection.

The timing of the second injection will be determined by the clinician and patient based on symptoms and will not be standardized.

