### Statistical analysis plan

The primary endpoint is the presence (Yes/No) of urinary tract infection 3 weeks post procedure. We will estimate the probability of urinary tract infection for both treatment groups. Baseline patient-characteristics data will be collected and tabulated. The trial design (crossover) will guarantee that the baseline covariates will be distributed similarly for both treatment groups. Carryover effect is minimized since the time between the first and second injections is sufficiently long for any residual treatment effect from the first period to wear off. For each treatment, the probability of UTI will be estimated and presented with 95% Wilson confidence intervals. We aim to establish non-inferiority of EDA to PPA with the non-inferiority margin of 10 percentage points. We will estimate the proportion of patients who will have infection with EDA but not with PPA.

Sample size and power were computed using the method described in Chow et al . To compute the sample size, we need to specify, in addition to the usual parameters (type I error rate of 5%, type II error rate of 10%, non-inferiority margin of 0.10, and difference under the alternative of 0), the variance of difference, which takes value of 1 if only EDA is successful, -1 if only PPA is successful, and 0 if EDA and PPA yield the same outcome. This variance, in turn, depends on the true probability of infection with EDA and PPA and also concordance of the result (success/failure) within a given patient. Under a pessimistic scenario where P[infection] is 25% and 35%, and the concordance is weak (Knowing the result of other treatment only changes the probability by 5 percentage points for the patient), the variance is 0.40, and the corresponding sample size is 68. Even if the true P[infection] is 35% and 45%, we will maintain the excellent power as shown below in the Table.

Power with n=68

P[infection] with EDA	0.25	0.25	0.35	0.35
P[infection] with PPA	0.35	0.35	0.45	0.45
Concordance	+0.05	+0.10	+0.05	+0.10
Power	90%	92%	83%	86%

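### Both regimens are recognisable and no masking is described, so a UTI endpoint that needs reported symptoms and a discretionary culture can be ascertained differently by regimen, in either direction

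*Combined protocol and SAP*

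**What the plan says.** All references are to the combined protocol and SAP.

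- **Regimens** (Day of Injection, Antibiotic protocol): "Patients randomized to the experimental arm will receive a single dose of trimethoprim/sulfamethoxazole (800/160mg) peri-procedurally". The control arm also has a peri-procedural dose and is then prescribed a further three days. No placebo is mentioned.
- **Second period** (2nd Injection): "patients will receive the treatment from the arm NOT received after the first injection".
- **Masking**: none is described in any section for patient, clinician or assessor. The Randomization section covers only regimen order and block sizes. The plan does not call itself open-label either.
- **Endpoint** (Statistical analysis plan): "The primary endpoint is the presence (Yes/No) of urinary tract infection 3 weeks post procedure". The note under the 3-week Post-Procedure Visit sets the threshold at 10^5 or more "bacterial colonies in the presence of symptoms".
- **Culture after the procedure** (3-week Post-Procedure Visit, Urinary tract infection): "If a patient reports symptoms concerning for UTI, urine culture and antibiotic treatment will be ordered at the discretion of the clinician". The list of visit procedures also leaves the culture to the physician's judgement.
- **Culture before the procedure** (Initial Visit, Urinary tract infection): "On the day of injection a voided urine specimen will be obtained from all patients and sent for urine culture".
- **Other capture** (3-week Post-Procedure Visit): every patient has a urinalysis, questionnaires and a survey, is told how to report symptoms, and has outside culture and antibiotic records retrieved.

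**The concern.** A period counts as UTI only after three steps: the patient reports symptoms, a culture is taken, and someone decides that the symptom criterion is met. The first two are in the hands of people who can know which regimen was given. For the third, the plan names neither a decision-maker nor a symptom list. All participants have refractory overactive bladder, so urgency or frequency alone does not separate infection from the underlying condition.

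If reporting, culturing or classification differs by regimen, part of the observed difference reflects ascertainment and not infection. In a non-inferiority comparison this can produce a false claim or hide a true one, depending on its sign and on which regimen is being tested.

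**Working it through.** **Step 1. Can the regimen be known?** A take-home prescription in one arm only, with no placebo, identifies the regimen to patient and clinician in period 1. Because period 2 is always the opposite regimen, it is known before it starts.

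**Step 2. Where can that knowledge enter the endpoint?** The definition has two parts, and both must hold.
- *Missed events.* A count of 10^5 exists only if a culture was taken. A true infection that is not reported, or is reported and not cultured, cannot meet the definition. The plan also does not say how a period treated without a culture is coded.
- *Added events.* Bacteriuria at or above 10^5 together with symptoms due to overactive bladder can be counted as UTI. More culturing under one regimen finds more of these.
- *What cannot happen.* Symptoms alone, without the count, do not make an event.

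**Step 3. Does the crossover cancel it?** Let p be a true UTI rate common to both regimens, and d(E) and d(P) the probabilities that a true UTI is recorded under the extended course and the single dose. The expected difference within a patient is

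p × d(E) − p × d(P) = p × [d(E) − d(P)].

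It is the same whether the extended course comes first or second, so averaging over the two sequences does not remove it. The crossover balances patient characteristics; it does not balance a bias that follows the regimen.

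**Step 4. How large could the shift be?** The plan has no figure for detection by regimen, so there is none to reproduce and the gaps are assumptions. For p I use 25%, 35% and 45%, the rates in the SAP power table, as a common true rate. Shift = p × gap. The last column is the gap that equals the SAP's 10-point margin, 0.10 / p.

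| True rate p | Gap 10 points | Gap 20 points | Gap equal to the margin |
|---|---|---|---|
| 25% | 2.5 points | 5 points | 40 points |
| 35% | 3.5 points | 7 points | 29 points |
| 45% | 4.5 points | 9 points | 22 points |

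This covers missed events only. The documents give nothing from which to size the added ones.

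**Step 5. What would a shift do to the test?** Inputs from the SAP: n = 68, variance of the paired difference 0.40, margin 0.10, type I error 5%, taken here as one-sided because the SAP does not say. The plan's own sample size does not reproduce with the usual paired formula: 0.40 × (1.645 + 1.282)² / 0.10² = 342.6, or 343 patients, and n = 68 gives 36.7% power, not 90%. That is a separate matter; here only the change caused by a shift is of interest. The standard error is √(0.40/68) = 0.0767.

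- Shift in favour of the tested regimen: probability of a false claim at the margin = Φ(shift / 0.0767 − 1.645). For shifts of 0, 2.5, 5 and 7 points: 5%, 9.4%, 16.0% and 23.2%.
- Shift against it: power at a true difference of 0 = Φ((0.10 − shift) / 0.0767 − 1.645). For the same shifts: 36.7%, 25.2%, 16.0% and 10.5%.

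**The case against.** The strongest reply is that the endpoint is anchored in a laboratory count. Attributing urgency to infection cannot by itself create an event. Every patient, under either regimen, also has a urinalysis, questionnaires and a survey at 3 weeks, and outside records are retrieved. Comparing antibiotic durations without a placebo is a legitimate pragmatic choice. Once a count and a symptom record exist, coding is close to mechanical, so masking that step adds little.

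Much of this stands. The count limits false positives, and the uniform procedures lessen differential capture. But neither the urinalysis nor the survey leads to a culture by rule, and outside records contain only the cultures that someone ordered. These safeguards do not equalise culturing. Masked coding cannot recover a culture that was never taken, which is why a common culture criterion has to be part of the remedy.

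Two further limits apply. That the trial is open is inferred from the absence of placebo and masking; the plan does not state it. And the sentences on allergic patients describe three-day courses without naming an arm, so it is unclear whether the regimens differ visibly for them. Those sentences must be reconciled with the two-arm description.

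A reader might infer that the bias must inflate UTI under the single dose, because patients and clinicians would be more alert without a course of tablets. The documents do not establish a direction: recent antibiotics may also change how readily a culture is sent after the extended course.

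**Conclusion.** The plan lets people who can know the regimen influence whether the primary endpoint is recorded, in both periods, and contains nothing that makes ascertainment the same under both regimens. That follows from the text. The size does not: the shifts of 2.5 to 4.5 points (10-point gap) and 5 to 9 points (20-point gap) rest on assumed detection gaps and on a true rate common to both regimens.

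A reader might infer that the bias could use up the whole margin. That would need a detection gap of 22 to 40 points, and nothing in the documents supports one that large. Nor can it be said that the bias favours the trial's claim. The Antibiotic protocol calls the single dose experimental, while the SAP sets out to show that the extended course is non-inferior to it. The same shift helps one claim and hurts the other, so these passages must be reconciled before the consequence can be named.

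The point is worth acting on because the endpoint is primary and the remedy is cheap.

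**What to change.** 1. State in the protocol that the trial is open-label and that endpoint coding is masked.
2. Define one fixed list of UTI symptoms and apply it identically under both regimens, at the 3-week visit and at any earlier symptom report. Use it both for the symptom part of the endpoint and as the common criterion for obtaining the endpoint culture. Treatment decisions are not affected.
3. Have the patient complete the already planned 3-week survey, including that list, before the clinician encounter.
4. Have an existing study-team member code UTI yes or no for each period from an extract of dated culture results and symptom items, with regimen, period and study-antibiotic lines removed. The written coding rule should also cover periods treated without a culture.
5. Report culture rates by regimen, so that any remaining difference in ordering is visible.

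The cost is a short coding rule, a redacted extract, some data handling and any additional cultures that the common criterion brings. No placebo, extra visit or new staff is needed. The limitation is that patient reporting, and any discretion left in ordering cultures (including by outside providers), stay unmasked. The bias is reduced, not removed.

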**Protocol/SAP**

**October 6, 2018**

# Research Protocol

## Initial Visit

**Study population.** Enrollment is planned to achieve a total of 68 patients, with each subject undergoing two injections. All patients will receive 2 injections over the study time period as part of this cross-over study. Participants must be adult patients (age 18 or older) with medication-refractory non-neurogenic OAB subject to the following inclusion and exclusion criteria (Table 1). Patients who elect to proceed with intravesical BTX-A injection as third line therapy, and are deemed appropriate for treatment by the clinician, will be considered for eligibility. Patients presenting for injection will be screened and consented prior to the first injection, and this consent will apply for the duration of the study (over two injections).

**Demographic and clinical data:** Participants will complete a standardized questionnaire assessing demographics and pertinent medical history including surgical history, current and past OAB therapy, history of urinary tract infections (UTIs) and urinary retention, and self-reported diagnoses of comorbid medical conditions. We will supplement this information with abstracted data from electronic medical records on past medical and surgical history, urinalysis, urine culture data, and post-void residual.

**Note:** Recurrent UTI will be defined as three or greater culture documented UTIs within a 12 month period.

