### Day of Injection

#### **New Patients:**

New patients will undergo complete history and focused physical exam. PVR will be obtained at initial clinic visit. If PVR has not performed or is not on file on the day of injection, PVR will be obtained prior to injection. If PVR >250cc, it will be repeated after double void. If again greater than >250cc, patient will be excluded from enrollment for that injection. Physician will be responsible for determining if patient has symptomatic UTI on the day of injection, and exclude the patient if appropriate (UA will be utilized in making this decision).

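### Duration of benefit is summarised only in patients who are reinjected, so it is biased, in a direction the plan cannot determine, if anyone does not return

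*Combined protocol and SAP*

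**What the plan says.** The Treatment success paragraph under 3-week Post-Procedure Visit states: "Efficacy of injection will be assessed via inter-injection times for patients receiving multiple injections". It adds that these patients "will be followed for the duration of the study period". The same sentence is repeated under 3-month Post-Procedure Phone Call. No section gives the length of the study period.

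The 2nd Injection section leaves the interval to need: "The timing of the second injection will be determined by the clinician and patient based on symptoms and will not be standardized".

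The Initial Visit section sets the intention for all patients: "All patients will receive 2 injections over the study time period as part of this cross-over study". The planned total is 68, with no stated allowance for patients who do not come back.

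The Statistical analysis plan does not mention inter-injection time and has no rule for censoring or missing data. Its primary endpoint is a different one: "The primary endpoint is the presence (Yes/No) of urinary tract infection 3 weeks post procedure".

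**The concern.** Reinjection marks the return of symptoms, so the interval is a time to event. Calculating it only in patients who have had the event conditions on the outcome. A patient still in relief when the study closes contributes nothing, although that patient has the longest duration. A patient who gives up after a poor result also contributes nothing, although that patient has one of the shortest.

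At stake is the plan's only measure of how long an injection works beyond 3 months. If non-return is more than occasional, the reported duration describes a selected group and cannot be read as the duration for the patients who were injected.

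**Working it through.** The plan gives no figure for inter-injection time, so there is none to reproduce. The size of the problem can be shown only under assumptions.

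**Inputs from the documents:** the measure is limited to reinjected patients; reinjection is symptom-driven; the follow-up length is not given; 68 patients.

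**Assumed inputs:** time to reinjection T follows a gamma distribution with coefficient of variation 0.5 (shape 4) and mean 8 or 10 months (scale 2 or 2.5). Follow-up F is 9 to 36 months. Where used, a fraction q of patients stop for poor response or harm after 0 to 3 months of benefit and are not reinjected.

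**Step 1: only lasting benefit or study end prevents return.** Let G(t) be the probability that T ≤ t. The proportion returning is G(F), and the returners' median r solves G(r) = G(F)/2. For shape 4, G(t) = 1 − e^(−x)(1 + x + x²/2 + x³/6), with x = t/scale.

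Example, mean 8 and F = 12: x = 6, so G = 1 − e^(−6) × (1 + 6 + 18 + 36) = 1 − 61 × 0.00248 = 0.849. Solving G(r) = 0.424 gives r = 6.64, against a true median of 7.34.

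| Follow-up (months) | Mean 8: returning | Mean 8: returners' median (true 7.34) | Mean 10: returning | Mean 10: returners' median (true 9.18) |
|---|---|---|---|---|
| 9 | 66% | 5.79 (−1.6) | 48% | 6.25 (−2.9) |
| 12 | 85% | 6.64 (−0.7) | 71% | 7.50 (−1.7) |
| 18 | 98% | 7.24 (−0.1) | 93% | 8.76 (−0.4) |
| 24 | 99.8% | 7.33 (−0.01) | 98.6% | 9.10 (−0.08) |
| 36 | 100% | 7.34 (0) | 99.97% | 9.18 (0) |

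**Step 2: a different shape.** For a Weibull with shape 2 and median M, G(F) = 1 − 2^(−(F/M)²). With M = 9, 71% return by 12 months with median 7.15 (−1.9), and 94% by 18 months with median 8.60 (−0.4). With M = 12, 50% return by 12 months with median 7.73 (−4.3); at 24 months the median is 11.46 (−0.5). The pattern is the same, and the bias grows as benefit lengthens relative to follow-up.

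**Step 3: some patients stop for poor response or harm.** Take mean 8, F = 18 and q = 0.20. The true median over all injected patients solves 0.20 + 0.80 × G(t) = 0.50, so G(t) = 0.375 and t = 6.20. The returners' median is still 7.24, so it is 1.04 months too long.

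The bias is zero when as many patients are lost from the short end as from the long end: q = (1 − q)(1 − G(F)), which gives q = (1 − G(F))/(2 − G(F)). For 9, 12 and 18 months of follow-up, the sign changes at:

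- Mean 8: 0.342/1.342 = 25%, 0.151/1.151 = 13%, and 0.021/1.021 = 2%.
- Mean 10: 0.515/1.515 = 34%, 0.294/1.294 = 23%, and 0.072/1.072 = 7%.

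**Step 4: does censoring repair Step 1?** With mean 8, n = 68, staggered entry giving 6 to 24 months of follow-up, and no poor-response stoppers, simulation gives a returners' median of 6.71 and a Kaplan-Meier median of 7.36, against the true 7.34.

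**The case against.** The strongest reply is that the plan intends everyone to return. If all 68 patients have two injections, the interval is complete for each of them and nobody is dropped. That is correct, and the bias arises only through non-completion, which the documents do not quantify. But it is an enrolment intention, not an analysis rule. The limit to patients with multiple injections would be unnecessary if return were certain. The protocol also foresees one way an injection can be missed. After a repeated high post-void residual, the New Patients section says "If again greater than >250cc, patient will be excluded from enrollment for that injection", and the 2nd Injection section applies the same procedures again.

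A second reply is that the text names a measure, prescribes no estimator, and does not rule out censoring. This is fair. The gap is an absent rule combined with wording that, followed literally, uses returners only.

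Third, other efficacy information exists. For follow-up the plan states: "Follow up visit will consist of urinalysis, ultrasound PVR, patient-reported questionnaires, and recording of adverse events". The symptom and quality-of-life instruments are planned for all patients at 3 weeks and 3 months, whether or not they are reinjected. This stands as a limit on the consequences, although those instruments do not measure how long benefit lasts after 3 months.

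Fourth, long follow-up removes the truncation. Under the gamma assumptions it nearly does by 24 to 36 months, but the plan promises no such length, and longer follow-up does not recover patients who stopped for poor response.

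**Conclusion.** The point holds as a minor one. As worded, the efficacy rule yields a biased duration whenever some patients are not reinjected. The bias is downward if they are still benefiting or the study ends first, and upward if they stopped for poor response or harm.

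Under the gamma assumptions with no poor-response stoppers, the median is 0.7 to 2.9 months too short with 9 to 12 months of follow-up, and within 0.1 month of the truth at 24 to 36 months. With a 12-month Weibull median the shortfall reaches 4.3 months at 12 months of follow-up. All these figures rest on durations, windows and stopping rates that the documents do not supply.

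A reader might infer two stronger conclusions. One is that the rule necessarily understates duration. It does not: in the gamma cases with 9 to 18 months of follow-up, the sign reverses once 2% to 34% of patients stop early, depending on duration and window. The other is that the rule dilutes a difference between antibiotic regimens. No section plans to compare regimens on this measure, and with the sign of the bias open, dilution could not be assumed anyway.

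The primary infection endpoint and its sample size do not use inter-injection time.

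**What to change.** Replace the sentence in both Treatment success paragraphs, and add the analysis to the Statistical analysis plan:

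- **Measure and population:** time from first to second injection in all patients who receive the first injection.
- **Censoring:** at last contact or study end for patients not reinjected who have not stopped for lack of effect or harm. State the length of the study period or a closing date.
- **Competing event:** stopping for lack of effect or harm. Censoring these patients would treat them as possibly still benefiting.
- **Summary:** cumulative incidence of reinjection and of the competing event, or Kaplan-Meier if no competing events occur. Report the number not reinjected, by reason.
- **If regimens are ever compared on this measure:** compare by the arm received at the first injection. Two injections give one interval per patient, so there is no within-patient comparison.

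Injection dates are already needed for the planned measure. The added cost is small: the date of last contact and the reason for non-return must be taken from the medical record, because the last scheduled contact after an injection is the 3-month call. If every patient returns as planned, the new analysis gives the same answer as the present rule.
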